1.0 SPECIFIC AIMS

Malignant adrenal pheochromocytoma (PHEO) and extra-adrenal pheochromocytoma (paraganglioma, PGL) remain fatal cancers for the majority of patients, with an average survival of 4.5 years. ¹³¹I-metaiodobenzylguanidine (¹³¹I-MIBG) is a norepinephrine analog that concentrates in adrenergic tissue and therefore holds promise for cell-specific treatment of malignant PHEO/PGL. ¹³¹I-MIBG is active against malignant PHEO/PGL. The associated hematopoietic toxicity can be abrogated with autologous stem cell rescue. ¹³¹I-MIBG given in doses of 8-12 mCi/kg with stem cell rescue, if necessary, is a reasonably safe and effective palliative therapy for patients with refractory or relapsed malignant PHEO/PGL.

Primary Aims:

- Provide palliative therapy for patients with malignant PHEO/PGL.
- Gain more information about acute and late toxicity of ¹³¹I-MIBG therapy for patients who have metastatic PHEO/PGL.

Secondary Aim:

• Obtain disease and symptom responses on patients with malignant PHEO/PGL who are not eligible for other therapy of higher priority.

2.0 BACKGROUND AND RATIONALE

Pheochromocytomas (PHEO) and paragangliomas (PGL) are rare tumors, with an incidence of 2-8 cases per million annually. These tumors develop in both children and adults. About 15-20% metastasize. Chemotherapy for this tumor usually consists of a combination of cyclophosphamide, vincristine, and dacarbazine delivered over two days and repeated every 3 weeks. Such combined chemotherapy is ineffective for the majority of patients with metastatic PHEO/PGL. A few patients with malignant PHEO have experienced remissions with sunitinib, but the drug may produce severe toxicity and the experience with that drug is limited. Those patients who do experience a remission with chemotherapy must continue it indefinitely to stay in remission. However, most such patients experience such severe side effects from the chemotherapy (marrow suppression, neuropathy, etc) that their chemotherapy must be discontinued. Thus, chemotherapy is either ineffective or intolerable for the vast majority of patients with metastatic PHEO/PGL.

2.1 Previous Human Experience with ¹³¹I-MIBG

Meta-iodobenzylguanidine (MIBG) is a guanethidine derivative structurally resembling norepinephrine. Originally synthesized by Short and Darby as a potential antihypertensive agent [1], MIBG was investigated by Wieland and his colleagues at the University of Michigan as a potential radiolabeled adrenergic neuron imaging agent [2]. MIBG was shown to have marked affinity for, and concentration in, the adrenal medulla, where it is subsequently stored in

neurosecretory granules [3-5].

MIBG can be labeled with radioactive isotopes of iodine, suitable for diagnostic imaging applications (¹²³I), or for both imaging and therapy (¹³¹I). MIBG has been extremely useful for the scintigraphic localization of pheochromocytomas and for the characterization of incidentally discovered adrenal masses [6-8]. MIBG has also been shown to concentrate in several neoplasms of neuroectodermal origin, particularly PHEO/PGL and neuroblastoma. Diagnostic MIBG scintigraphy is currently used routinely for PHEO/PGL disease staging and response evaluation [2,9-12].

¹³¹I-MIBG has undergone extensive single institution, and more recently, cooperative clinical trials for the treatment of malignant pheochromocytoma and neuroblastoma [13-19]. This includes trials at UCSF, Children's Hospital of Philadelphia, and University of Michigan, as well as in the NANT consortium. The results from these trials show that MIBG is active against refractory neuroblastoma with a response rate of 30-40% and is highly effective therapy for disease palliation [13,14,15,17,20,21,22,23,24]. Non-hematologic toxicity, even at substantial doses of MIBG, has usually been minimal and included brief nausea and vomiting, mild reversible myelosuppression, transient hepatic dysfunction, adrenal insufficiency (in one patient), and chemical hypothyroidism. The most significant toxicity has been prolonged thrombocytopenia, most marked in patients with tumor in the bone marrow, and more transient neutropenia. Thus, ¹³¹I-MIBG appears to be a highly specific and active agent for treatment of human neuroblastoma and PHEO/PGL, but the optimal method for delivering this novel therapy remains to be determined.

2.2 UCSF Experience

Fifty-five patients with metastatic PHEO/PGL have been treated with doses of ¹³¹I-MIBG ranging from 492 mCi to 1160 mCi. Prior publications have described our first 12 patients and first 30 patients. We now have response data from the first 50 patients with metastatic PHEO/PGL treated at UCSF with ¹³¹I-MIBG:

Cumulative ¹³¹I-MIBG ranged from 492-3191 mCi. Autologous hematopoeitic stem cells were collected and cryopreserved prior to treatments with ¹³¹I-MIBG in doses >12 mCi/kg or >500 mCi/kg. Thirty-five patients were treated once, while 15 patients received two or three treatments. By RECIST criteria, the overall combined complete response (CR) plus partial response (PR) rate was 22%. Additionally, 35% of patients achieved a CR or PR response in at least one measure of hormonal response, without any progressive disease, and an additional 8% of patients maintained stable disease >12 months. Thirty-five percent of patients experienced progressive disease within one year following therapy. The estimated 5-year overall survival was 64%. Toxicities included: grade 3-4 neutropenia (87%) and thrombocytopenia (83%).

Grade 3-4 non-hematologic toxicity included: pulmonary embolism (n=1), fever with neutropenia (n=7), acute hypertension (n=10), infection (n=2), hypogonadism (n=6).

Two patients developed bronchiolitis obliterans organizing pneumonia (BOOP) after ¹³¹I-MIBG doses of 845 mCi (8.1 mCi/kg) and 1062 mCi (16.9 mCi/kg) respectively; both patients recovered. Two patients developed acute respiratory distress syndrome (ARDS) after ¹³¹I-MIBG doses of 1,160 mCi (18 mCi/kg) and 1,030 mCi (12.1 mCi/kg) respectively. One patient (with a heavy secretory tumor burden and severe nephrotic syndrome) died from ARDS. Two patients developed myelodysplastic syndrome (MDS) with acute myelogenous leukemia after partial remissions lasting 5 and 2 years following ¹³¹I-MIBG at cumulative doses of 1,712 mCi and 1832 mCi respectively.

3.0 SUBJECT RECRUITMENT AND SELECTION

This is a best available therapy/compassionate use study designed to determine the palliative benefit and toxicity of ¹³¹I-MIBG in patients with progressive pheochromocytoma (PHEO) or paraganglioma (PGL) who are not eligible for therapies of higher priority. Patients may receive a range of doses depending on stem cell availability and tumor involvement of bone marrow. Response rate, toxicity, and time to progression and death will be evaluated. All eligible patients will be offered participation in this study regardless of gender or race.

3.1 Eligibility criteria

- **3.11 Diagnosis:** Refractory or relapsed PHEO/PGL with original diagnosis based on tumor histopathology or the finding of PHEO/PGL tumor cells in the bone marrow. The diagnosis may also be based upon the presence of high plasma fractionated metanephrines or high urine catecholamines/metanephrines with diagnostic MIBG uptake.
- **3.12** Age: > 2 years and able to cooperate with radiation safety restrictions during therapy period.
- **3.13 Disease status:** It must be determined that either the PHEO/PGL tumors are not amenable to safe surgical resection or are metastatic. Disease evaluable by MIBG scan must be present within 6 weeks of study entry and subsequent to any intervening therapy.

3.14 Life Expectancy: greater than 3 months.

3.15 Lanksy and Karnofsky Performance Status: 70% or higher.

3.16 Stem cells: Patients must have an autologous hematopoietic stem cell product available for re-infusion after MIBG treatment at doses of >12 mCi/kg *or* >500 mCi (whichever is smaller) if needed. The minimum quantity for purged or unpurged peripheral blood stem cells is $1.0 \ge 10^6$ CD34+ cells/kg (optimum $\ge 2 \ge 10^6$ CD34+ cells/kg). The minimum dose for bone marrow is $1.0 \ge 10^8$ mononuclear cells/kg (optimum $> 2.0 \ge 10^8$ mononuclear cells/kg). If no stem cells are available, then the dose of 131 I-MIBG should

be $\leq 12 \text{ mCi/kg}$ and $\leq 500 \text{ mCi}$. (Note: Due to the nature of radioisotope decay, the administered dose limitations may have an inherent tolerable variability of $\pm 1.2 \text{ mCi/kg}$ or $\pm 50 \text{ mCi}$.)

3.17 Prior Therapy: Patients may enter this study with or without having had other therapy for recurrent tumor. Patients may be treated who have not had chemotherapy or radiation therapy. Patients may also be treated who have failed to respond to standard chemotherapy or radiation therapy. Patients must have fully recovered from the toxic effects of any prior therapy. At least 2 weeks should have elapsed since any anti-tumor therapy and the patient must meet hematologic criteria below. Three months should have elapsed in the case of completing radiation to any of the following fields: total craniospinal, total abdominal, whole lung, total body irradiation). Cytokine therapy (eg G-CSF, GM-CSF, IL-6, erythropoietin) must be discontinued a minimum of 24 hours prior to MIBG therapy. Prior ¹³¹I-MIBG therapy is allowed if > 3 months previous and if the patient has adequate hematopoietic stem cells available for planned doses of >12 mCi/kg *or* >500 mCi. Cumulative lifetime dose of ¹³¹I-MIBG, including the planned treatment, should not exceed 36 mCi/kg.

3.18 Organ Function

- 3.181 Liver function: bilirubin < 2x upper limit of normal (ULN). Exception: Gilbert syndrome); AST \leq 10x ULN.
- 3.182 Kidney function: Creatinine $\leq 2x$ ULN.
- 3.183 Hematopoietic Criteria: Patients must have adequate hematopoietic function (without transfusion): ANC \geq 750/µL; Platelets \geq 50,000/µL if stem cells are not available; if stem cells are available, the patient should be independent of platelet transfusions with a platelet count of at least 20,000/µL. Hemoglobin \geq 10g/dl at time of treatment (transfusion allowed). Patients with granulocytopenia and/or thrombocytopenia due to tumor metastatic to the bone marrow may be eligible after discussion with [name] or designee.
- 3.184 Normal lung function as manifested by no dyspnea at rest or exercise intolerance, no oxygen requirement.
- 3.185 No clinically significant cardiac dysfunction, normal EKG and EJ >50%

3.186 Signed informed consent: The patient and/or the patient's legally authorized guardian must acknowledge in writing that consent to become a study subject has been obtained, in accordance with institutional policies approved by the U.S. Department of Health and Human Services.

3.2 Exclusion criteria

- 3.21 Patients with disease of any major organ system that would compromise their ability to withstand therapy. Any significant organ impairment should be discussed with the Study Chair or Vice Chair prior to patient entry.
- 3.22 Because of the teratogenic potential of the study medications, no patients who are pregnant or breast feeding will be allowed. Patients of childbearing potential must practice an effective method of birth control while participating on this study, to avoid possible pregnancy.
- 3.23 Patients who are on hemodialysis.
- 3.24 Patients with active infections that meet grade 3-4 toxicity criteria.
- 3.2 **Registration procedure:** Call [name] [contact] or [name] [contact] prior to treatment and fax a copy of the consent form to [name] [contact].

4.0 TREATMENT

4.1 On Study: Disease status and pre-therapy organ evaluation will be done as detailed in Section 5.0. Each patient will undergo a diagnostic quality ¹³¹I- or ¹²³I–MIBG scan within 6 weeks of entry onto study and without other intervening anti-tumor therapy. See Section 5.0 Required Observations.

4.2 Treatment

- **4.21** ¹³¹I-MIBG Therapeutic Administration. Therapeutic ¹³¹I-MIBG will be synthesized at Nuclear Diagnostic Products (NDP; Rockaway, New Jersey) with specific activities of 9-18 Ci/mmole. The therapeutic dose: 8-12 mCi/kg (maximum 800 mCi \pm 10% at investigator's discretion; any dose > 500 mCi \pm 10% requires stored stem cells) will be diluted in 25 ml of normal saline, and will be infused intravenously through a patient's peripheral or central line over 120 minutes. The patient will remain in a radiation protected isolation room until radiation emissions are \leq 2 mr/hr at a 1 meter distance or meets institutional and state guidelines. This usually takes 4-6 days. In all cases, special shielding will be equipped in the room to minimize exposure to the outside environment and personnel will observe institutional radiation safety precautions.
- **4.22** Bladder protection. It is recommended that a urinary catheter be inserted prior to the MIBG infusion and retained for a minimum of 72 hours or until the patient is released from radiation isolation if incontinent. The catheter will prevent accumulations of large amounts of radioactivity in the bladder. Drainage of urine will be into a continuously

Principal Investigator: [name].

Compassionate Use of ¹³¹I-MIBG for Patients with Malignant Pheochromocytoma

running toilet or into a sterile bag housed in lead shielding; the bag will be emptied every 3-12 hours depending on the size of the patient and the rate of urine output. Intravenous fluids will be administered at 75-125 ml/m²/hour to help maintain urine flow and isotope excretion for at least 72 hours. In case the patient is unable to cooperate with this catheter and the isolation, sedation and temporary placement of a spica body cast may be necessary.

- **4.23** Thyroid protection. For the therapeutic MIBG administration, KI solution will be administered in a loading dose of 6 mg/kg p.o. the night before the MIBG injection, then 1 mg/kg/dose q 4h days 0-7, then 1 mg/kg/day through day 45 post injection. Potassium perchlorate will be given as an additional blocking agent, beginning with 8 mg/kg loading dose on the evening before the MIBG injection, then 2 mg/kg, p.o., q 6h for 5 days following the MIBG. The doses may be reduced in the event of gastrointestinal intolerance.
- **4.24** Imaging. For all patients, a scintigraphic MIBG imaging study, comparable to the diagnostic scan, will be done near the time of discharge, usually on day 4 or 5 post-treatment. This scan is performed to confirm tumor uptake and also to survey for occult sites of disease. Patients will not receive any MIBG injection for this scan. Some patients may elect to participate in a separate organ or tumor dosimetry study, which would require a separate consent and extra images.
- **4.25** G-CSF. Patients whose ANC is less than 500/uL after MIBG infusion will begin G-CSF 5 mcg/kg/day (or an equivalent single dose of Neulasta) subcutaneously until neutrophil recovery.

4.3 **Post-Treatment Evaluation**

Post-treatment evaluation will be performed 8-12 weeks after treatment. Required studies are detailed in Section 5.0

4.31 Toxicity. Complete FDA Form 3500A (Medwatch) for grade 3 and 4 toxicities except expected hematologic toxicities and fever. Deaths occurring <6 weeks post treatment should be reported.

4.4 Criteria for hematopoietic stem cell infusion.

It is recommended that a patient receive an infusion of a portion of their cryopreserved autologous hematopoeitic stem cells if they develop grade 4 hematologic toxicity following ¹³¹I-MIBG therapy and continue to have an ANC < 200/uL on G-CSF/Neulasta without signs of recovery for > 2 weeks. In addition, any patient requiring platelet transfusions more than two times weekly for 2 consecutive weeks will receive hematopoietic stem cell rescue. Stem cell infusion may occur sooner or later if indicated (i.e. due to an infectious or bleeding complication) after consultation with the Study Chair or designee.

4.5 Criteria for subsequent treatment. Patients may be eligible for additional ¹³¹I-MIBG therapies if they meet the following criteria:

- **4.51** Minimum of eight weeks from previous MIBG therapy on this study.
- **4.52** Response or stable disease after the first infusion. If patient responds with a CR to the first infusion, the patient may receive a second therapy as consolidation.
- **4.52** Meets all other criteria as outlined in eligibility and pre-treatment evaluation sections above except for platelet count. Patient may be thrombocytopenic, but requiring no more than 1 platelet transfusion per week to maintain counts above 20,000.
- **4.53** To receive a subsequent course at > 12 mCi/kg or > 500 mCi (\pm 10%), a patient must have cryopreserved hematopoietic stem cells available in sufficient quantity, as stated in 3.14.

5.0 **REQUIRED OBSERVATIONS**

Required observations listed are for toxicity and response monitoring. More frequent or additional tests should be ordered as clinically indicated.

Observation	Before or at Entry	Day 0-7 ¹	Day 7-56	Day 56-120
Physical Exam	Х			X
CBC with Diff, Platelet count	Х		Weekly ²	X
Urinalysis	Х			X
AST, ALT, T. Bilirubin, Albumin	Х		Weekly	X
BUN, creatinine	Х		Weekly	Х
Electrolytes	Х			X
Ca, Mg, Phos	Х			X
FT ₄ , TSH	Х			X
Serum β-HCG ³	Х			
Bilat BM Asp/Bx	Х			X ⁵
Tumor Imaging (CT or MR) ⁴	Х			Х
¹³¹ I-MIBG Infusion		Day 0		
MIBG Diagnostic Scan (REQUIRED)	Х			Х
MIBG whole body scan		Between D 3-7		
Urine fractionated catecholamines & metanephrines and	X^4			X

serum chromogranin A

- 1. No routine bloodwork or radiologic studies are required while patient is hospitalized in radiation protected environment unless clinically indicated. Patients with prior electrolyte imbalance should be monitored during the hydration.
- 2. Twice weekly CBC/Diff/Plt until ANC $>500/mm^3$ & Plt count > 20,000 x 3 days without transfusion.
- 3. Obtain for females 10 years of age and older or post-pubertal.
- 4. Tumor imaging = CT/MRI as needed for optimum visualization of all areas of bulk tumor (primary & metastasis). Must be performed ≤ 6 weeks prior to study entry. Repeat urine fractionated catecholamines & metanephrines and serum chromogranin A only if elevated pre-therapy. If the patient receives further therapy on other protocols at ANY TIME POINT, no further tumor studies will be subsequently required for this protocol.
- 5. BM aspirate/biopsy must be repeated only if positive at study entry

5.1. Recommended follow up observations:

CBC with differential and platelet count, ALT, AST, bilirubin, T_4 , TSH and MIBG scan every 3 months until 1 year post treatment, then q 6 months until progression, death or other therapy. Other disease evaluation as clinically indicated.

6.0 **RESPONSE CRITERIA**

All patients who are registered will be accounted for in the report of the results. Patients who complete one course of therapy will be evaluated for response at 2-4 months post treatment, or earlier if proceeding to other therapy. Volumetric measurable disease will be assessed with the same modality (MRI or CT scan) as was performed at the on study evaluation. The following disease status definitions will be used.

RECIST RESPONSE CRITERIA used for measurable soft tissue tumor

Overall response:

Response	Primary Tumor*	Metastatic Sites* [#]
CR	No Tumor	No tumor; catecholamines, metanephrines and chromogranin A all normal.
PR	Decreased >50%	All measurable sites decrease by $> 50\%$. Bones and bone marrow: number of positive bone sites decreased by $>50\%$; bone marrow tumor decreased by 50%

MR	No new lesions; >50% reduction of any measurable lesion (primary or metastases) with $<50\%$ reduction in any other; $<25\%$ increase in any existing lesion.
NR	No new lesions; <50% reduction but <25% increase in any existing lesion.
PD	Any new lesion; increase of any measurable lesion by >25%; previous negative marrow positive for tumor.

*Evaluation of primary and metastatic disease as outlined.

[#]One positive marrow aspirate or biopsy allowed for PR if this represents a decrease from the number of positive sites at diagnosis.

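### The stated dose of 8-12 mCi/kg does not fit the sections that foresee doses above 12 mCi/kg, or the 500 mCi limit for heavier patients without stem cells

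*Protocol*

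**What the plan says.** **The dose.** Section 4.21 states "The therapeutic dose: 8-12 mCi/kg (maximum 800 mCi", with 10% either way on that maximum at the investigator's discretion. The same sentence adds that "any dose > 500 mCi \pm 10% requires stored stem cells". Section 1.0 describes the treatment as reasonably safe and effective when "given in doses of 8-12 mCi/kg with stem cell rescue, if necessary".

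**Without stem cells.** Section 3.16 asks for a stored product above 12 mCi/kg or above 500 mCi, whichever is smaller. It then provides for patients who have none: "If no stem cells are available, then the dose of 131 I-MIBG should" be at most 12 mCi/kg and at most 500 mCi. It gives no lower limit. A note allows 1.2 mCi/kg or 50 mCi either way on these limits because of radioisotope decay.

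**Above 12 mCi/kg.** Section 3.17 allows earlier MIBG if enough stem cells are available for doses planned above 12 mCi/kg or 500 mCi. Section 4.53 sets the stem-cell condition "To receive a subsequent course at > 12 mCi/kg or > 500 mCi" and refers to 3.14 for the quantity.

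**Re-treatment.** Section 3.17 says that earlier MIBG "is allowed if > 3 months previous". Section 4.51 asks for a "Minimum of eight weeks from previous MIBG therapy on this study". The second paragraph numbered 4.52 adds that the patient "Meets all other criteria as outlined in eligibility and pre-treatment evaluation sections above except for platelet count".

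**The concern.** A site reading 4.21 would conclude that every patient receives between 8 and 12 mCi/kg. A site reading 3.17 or 4.53 would conclude that a course above 12 mCi/kg can be planned if stem cells are stored. A site with a heavier patient who has no stem cells would find the patient eligible under 3.16 but could not give the dose in 4.21. The text does not say whether that patient is treated below the range or not treated.

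The first stake is patient safety. Section 9.0 expects grade 4 hematopoietic toxicity in most patients and relies on stored stem cells, or on lower doses where there are none, to contain that risk. The second is interpretation. Learning more about acute and late toxicity is a primary aim in Section 1.0, and Section 7.0 intends the safety data to support FDA approval. Dose is the main exposure variable. If the administered doses can lie on either side of the stated range, a toxicity rate reported for 8-12 mCi/kg would describe a mixture of other doses as well.

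**Working it through.** The protocol states no limiting weight, so there is no figure of its own to reproduce. The check is a comparison of passages plus one division.

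**Inputs**
- Dose range 8-12 mCi/kg (1.0, 4.21).
- Limit without stem cells 500 mCi (3.16, and the condition in 4.21).
- Tolerance 10% (4.21), or 50 mCi and 1.2 mCi/kg (3.16).

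**1. Above the range**

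The tolerance takes 12 mCi/kg to 12 + 1.2 = 13.2 mCi/kg. It is described as a result of decay, so it concerns the gap between the activity intended and the activity given. A dose planned above 12 mCi/kg (3.17), or a course to be given above 12 mCi/kg (4.53), is not such a gap.

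The phrase above 12 mCi/kg or above 500 mCi can also be tested for what its first half adds. The two limits coincide at 500/12 = 41.7 kg.
- Above 41.7 kg, any dose over 12 mCi/kg already exceeds 500 mCi, so the per-kg half adds nothing.
- Below 41.7 kg, no dose within 8-12 mCi/kg reaches 500 mCi, so the per-kg half takes effect only at a dose outside the range in 4.21.

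At the nominal limits, then, the per-kg condition has an effect of its own only if doses above the range are possible.

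**2. Below the range, without stem cells**

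Limiting weight = activity limit (mCi) / per-kg dose (mCi/kg).

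| Activity limit | Weight above which 8 mCi/kg cannot be given |
|---|---|
| 450 mCi (500 - 10%) | 450/8 = 56.25 kg |
| 500 mCi (nominal) | 500/8 = 62.5 kg |
| 550 mCi (500 + 10%) | 550/8 = 68.75 kg |

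Dose per kg at the limit:

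| Weight | At 500 mCi | At 550 mCi |
|---|---|---|
| 70 kg | 7.14 mCi/kg | 7.86 mCi/kg |
| 80 kg | 6.25 mCi/kg | 6.88 mCi/kg |
| 100 kg | 5.00 mCi/kg | 5.50 mCi/kg |

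The tolerance moves the threshold but does not remove the conflict.

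**3. Secondary points**

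- Interval: eight weeks is 8 x 7 = 56 days, and three months is about 91 days. Section 4.51 sets the first for courses on this study. Section 3.17 sets the second for earlier MIBG and is not limited to treatment off study. The second 4.52 carries forward all other eligibility criteria except platelets, without saying whether 3.17 is among them.
- Cross-reference: 4.53 sends the reader to 3.14 for stem-cell quantity. Section 3.14 is life expectancy; the quantities are in 3.16.

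**The case against.** The strongest reply is that any absolute limit on a per-kg dose takes effect above some weight, and that this is its purpose. Section 3.0 says that doses will vary with stem-cell availability and marrow involvement, and Section 9.0 speaks of lower doses where stem cells are lacking. This stands in part: lower doses were clearly anticipated. But neither section gives a figure or says that a dose may fall below 8 mCi/kg, and the lower doses in 9.0 could equally be those near the bottom of the range.

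On doses above 12 mCi/kg, it is fair to say that 3.16 only attaches a condition and authorises nothing. That does not dispose of 3.17 and 4.53, which treat such doses as something to be planned or received.

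Several stronger readings are tempting, but the documents do not support them:
- **The 800 mCi maximum also contradicts the range.** It stands in the same sentence as the range and reads as an ordinary cap.
- **The eight-week and three-month intervals flatly contradict each other.** Section 4.51 can be read as the specific rule for on-study courses. What remains is that the text does not say so.
- **The platelet criterion is simply waived at re-treatment.** The second 4.52 makes an express exception and sets its own replacement limit.
- **The earlier patients in Section 2.2 show how often the conflict arises.** The four whose weight can be derived were reported for lung toxicity and all received more than 500 mCi. They are not a sample of patients without stem cells.

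**Conclusion.** The dose passages need to be reconciled on two counts. Sections 3.17 and 4.53 foresee doses above the only range that 1.0 and 4.21 state, and the decay tolerance does not explain this. Section 3.16 admits patients without stem cells who, above 62.5 kg nominally and 68.75 kg at the upper tolerance, cannot receive the stated minimum, and no passage says what then applies. The unclear re-treatment interval is a lesser point, and the wrong cross-reference is clerical.

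The weights rest only on the protocol's own limits. How many patients are affected cannot be worked out, because the protocol gives neither the expected weights nor the share without stem cells. A reader might infer that a planned analysis of the 8-12 mCi/kg dose is invalid. The protocol plans no dose-specific hypothesis: Section 7.0 lists progression-free survival, survival, response and toxicity. The consequence for analysis is narrower. Results should not be attributed to 8-12 mCi/kg without showing what was given.

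**What to change.** The investigators should:

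1. Reconcile 1.0, 3.16, 3.17, 4.21 and 4.53 into one statement of the permitted dose with and without stem cells. It should say whether doses above 12 mCi/kg or below 8 mCi/kg are within the protocol, and to which limits the tolerance applies.
2. State which interval applies to re-treatment on study, so that 3.17, 4.51 and 4.52 agree.
3. Correct the reference in 4.53 from 3.14 to 3.16.
4. Report toxicity and response against the administered mCi and mCi/kg, so that each conclusion is tied to the dose given.

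Which dose or interval is right is for the investigators; this review proposes none. The cost is amendment wording and a few tables from dosing data already recorded. No new visits, tests or patients are needed.

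### Sections 4.21 and 1.0 give a course dose of 8-12 mCi/kg, but Sections 3.16, 3.17 and 4.53 set stem-cell conditions for courses above 12 mCi/kg, so the protocol contradicts itself on whether such a course is permitted

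*Protocol*

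**What the plan says.** Two places in the protocol state a dose, and they agree.

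- Section 4.21: "The therapeutic dose: 8-12 mCi/kg (maximum 800 mCi", with a 10% margin on that maximum at the investigator's discretion. It requires stored stem cells for "any dose > 500 mCi" (again with 10%). It has no stem-cell trigger per kilogram.
- Section 1.0 describes treatment "given in doses of 8-12 mCi/kg with stem cell rescue, if necessary".

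Three other places set conditions for courses above 12 mCi/kg.

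- Section 3.16: "Patients must have an autologous hematopoietic stem cell product available for re-infusion after MIBG treatment at doses of >12 mCi/kg" or above 500 mCi, whichever is smaller. It holds the dose to 12 mCi/kg and 500 mCi only for patients without stem cells. A note allows 1.2 mCi/kg or 50 mCi either way and attributes this to isotope decay.
- Section 3.17, on patients with prior treatment, asks for "adequate hematopoietic stem cells available for planned doses of >12 mCi/kg" or above 500 mCi. It also sets a cumulative lifetime limit of 36 mCi/kg.
- Section 4.53 begins "To receive a subsequent course at > 12 mCi/kg or > 500 mCi", with a 10% tolerance, and requires cryopreserved cells in the quantity stated in 3.14. Section 3.14 is the life-expectancy criterion; the cell quantities are in 3.16.

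**The concern.** A limit that applies only when stem cells are absent is not the same as an unconditional upper end of a dose range. If 4.21 and 1.0 govern, no planned course can exceed 12 mCi/kg, and the per-kilogram stem-cell clauses have nothing planned to act on. If 3.16, 3.17 and 4.53 mean what they imply, 12 mCi/kg is a threshold that a patient with stored cells may pass, and 4.21 misstates the range.

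This matters to the statistics as well as to conduct. Section 1.0 makes acute and late toxicity a primary aim. Section 7.0 justifies the accrual of about 50 patients largely as safety data, and its suspension rules pool all patients without regard to dose. Toxicity rates can be interpreted only if the permitted exposure is defined. Section 3.12 admits patients from just above 2 years of age, so low body weights, where the readings diverge most, are in scope.

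The wrong cross-reference in 4.53 is a smaller fault, but it sends the reader to a criterion with no cell quantity at the point where a repeat course is being authorised.

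**Working it through.** The protocol has no figure of its own to reproduce here; the check compares its stated limits.

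**Inputs.** Range 8-12 mCi/kg and maximum 800 mCi plus or minus 10%, i.e. 720 to 880 mCi (4.21). Stem-cell trigger 500 mCi plus or minus 10%, i.e. 450 to 550 mCi (4.21). Trigger at the smaller of 12 mCi/kg and 500 mCi, with tolerance 1.2 mCi/kg or 50 mCi (3.16). Lifetime limit 36 mCi/kg (3.17). W is body weight in kg.

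**Step 1: upper dose.** If 12 mCi/kg is a ceiling, the upper dose is min(12W, 800). If it is only a threshold for stem cells, the upper dose for a patient with cells is 800 mCi, subject to the lifetime limit. The two meet where 12W = 800:

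- nominal: 800/12 = 66.7 kg
- at 720 mCi: 720/12 = 60.0 kg
- at 880 mCi: 880/12 = 73.3 kg

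| Weight (kg) | min(12W, 800) (mCi) | 800 mCi per kg | Ratio |
|---|---|---|---|
| 40 | 480 | 20.0 | 800/480 = 1.67 |
| 50 | 600 | 16.0 | 800/600 = 1.33 |
| 60 | 720 | 13.3 | 800/720 = 1.11 |
| 70 | 800 | 11.4 | 1.00 |

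**Step 2: lifetime limit.** For a patient with no prior treatment it binds before 800 mCi only below 800/36 = 22.2 kg. For a patient who has already had 24 mCi/kg, the remainder is 36 - 24 = 12 mCi/kg and the two readings coincide. It narrows the gap for some patients but sets no per-course ceiling.

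**Step 3: does the tolerance reconcile the sections?** Allowing 12 + 1.2 = 13.2 mCi/kg, the readings still diverge below 800/13.2 = 60.6 kg at the nominal maximum. The note in 3.16 concerns decay, whereas 3.17 refers to what is planned.

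**Step 4: stem-cell trigger.** Under 3.16 it is min(12W, 500); under 4.21 it is 500 mCi. These are equal from 500/12 = 41.7 kg upward (450/12 = 37.5 kg and 550/12 = 45.8 kg with the tolerance). Below that they differ: 12 x 30 = 360 against 500 mCi at 30 kg, and 12 x 40 = 480 against 500 mCi at 40 kg. The gap contains only doses above 12 mCi/kg, so it has no effect unless such a course is given.

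**Step 5: tolerances side by side.** Section 4.21 attaches 10% to 800 and 500 mCi. Section 3.16 gives 1.2 mCi/kg or 50 mCi. Section 4.53 puts 10% after the 500 mCi figure. Section 3.17 gives none.

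**The case against.** The best answer is that only 4.21 and 1.0 state a dose, and they agree. The other three clauses are preconditions: they say what must be in place if a dose exceeds a level, not that the level may be exceeded. The 800 mCi figure stands in the same phrase as 8-12 mCi/kg, so a reader who reaches 20 mCi/kg at 40 kg keeps half of that phrase and drops the other half. On this view the per-kilogram clauses are a redundant safeguard.

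That is a fair reading, but the text does not secure it. No clause gives 4.21 precedence, 3.16 imposes 12 mCi/kg only on patients without cells, and 3.17 speaks of planned doses. Section 3.0, which makes dose depend on stem-cell availability, does not decide the matter, because the 500 mCi trigger alone would also produce that dependence.

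Other parts of the objection stand. The 8-12 range already allows a 12/8 = 1.5-fold spread by design, so variation in dose is not itself the fault; the point concerns the ceiling. The 60 kg case, at 13.3 mCi/kg, is almost within the 13.2 tolerance. Doses are prescribed by a physician at one centre (Appendix 1) after registration by telephone, so divergence in practice is less likely than on paper.

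A reader might also infer that the lung cases in Section 2.2 show harm from this conflict, since three of four followed more than 12 mCi/kg. They do not. All four patients received more than 800 mCi (845, 1062, 1160 and 1030 mCi), three of them above even 880 mCi. One case counted as above 12 was at 12.1 mCi/kg, the fourth was at 8.1, and no denominators by dose are given.

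**Conclusion.** The contradiction is in the current text: the protocol both gives 12 mCi/kg as the top of the course dose and sets conditions for passing it. At the nominal maximum the upper dose is unsettled below 66.7 kg (60 to 73 kg with the 10% margin). The difference is 200 mCi at 50 kg and 320 mCi at 40 kg, with the lifetime limit also applying. These figures assume stored stem cells and enough remaining lifetime allowance. The protocol gives no weight distribution, so the number of patients affected is unknown.

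Two stronger readings should be avoided. It would be wrong to say that the stem-cell trigger is unsettled up to 67 kg: from 41.7 kg upward its nominal value is 500 mCi in every section. Nor does the protocol say that results will be reported as the toxicity of 8-12 mCi/kg; Section 7.0 specifies no such label.

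The cross-reference from 4.53 to 3.14 is an error on any reading.

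**What to change.** - Reconcile 4.21 and 1.0 with 3.16, 3.17 and 4.53 by stating in one place whether a planned course above 12 mCi/kg is permitted on this protocol, and make the other sections refer to that statement.
- State the stem-cell trigger once, including whether it has a per-kilogram limb, and use the same terms and tolerance in 3.16, 3.17, 4.21 and 4.53.
- Change the reference in 4.53 from 3.14 to 3.16.

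Which limit is right is a clinical decision for the sponsor's clinicians, and this review takes no position on it. The cost is one amendment with wording changes in up to five sections, and no added procedures or patients.
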